A total of 34 participants who satisfied the selection criteria were included. Simple random sampling was adopted for participant selection and random allocation into two groups was carried out using the lottery method to ensure unbiased group assignment. The participants were equally divided into two groups, the intervention group and the control group, with 17 participants in each group. Allocation concealment was maintained throughout the recruitment process to minimize selection bias.

Baseline assessments were conducted four weeks prior to the scheduled surgical procedure. Pre-test measurements included assessment of pelvic floor muscle strength using the Brink score, evaluation of overall functional status using the Karnofsky Performance Scale and assessment of recovery efficiency through the anticipated duration of hospital stay. All baseline assessments were performed before the commencement of the exercise intervention to ensure uniformity in data collection.

Participants allocated to the intervention group underwent a structured prehabilitation exercise program for a duration of four weeks prior to surgery. The prehabilitation protocol consisted of three supervised sessions per day, each lasting 20 minutes, amounting to a total of 60 minutes of exercise daily. The first session focused on aerobic training, which included activities such as walking, cycling and treadmill exercises based on the individual's choice, tolerance and fitness level. The second session emphasized pelvic floor muscle strengthening exercises, which were individualized and performed as two sets of ten repetitions to improve pelvic floor muscle activation and endurance. The third session consisted of resistance training exercises targeting both upper and lower limb muscle groups using appropriate equipment also performed as two sets of ten repetitions. Exercise intensity and progression were individualized based on the participant's functional capacity and clinical status.

Participants in the control group received a generalized standard exercise protocol for four weeks prior to surgery. This protocol included free exercises, breathing exercises

and walking, delivered in three daily sessions similar in duration to the intervention group. However, no structured or targeted prehabilitation components such as resistance training or specific pelvic floor muscle strengthening were included in the control protocol.

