Following surgery, participants in both groups underwent standardized postoperative rehabilitation for a period of two weeks. Postoperative rehabilitation included breathing exercises, pelvic floor strengthening exercises such as Kegel exercises and pelvic bridging and core strengthening exercises aimed at promoting early mobilization, improving functional recovery and preventing postoperative complications. The postoperative rehabilitation protocol was uniform for both groups to ensure comparability. Post-intervention assessments were conducted as per the study timeline after two weeks to evaluate the effectiveness of the intervention.

Materials Required

The materials required for the study included basic exercise and assessment equipment. For the intervention group, resistance bands, weight cuffs, dumbbells and a Swiss ball were used to perform aerobic, resistance and pelvic floor strengthening exercises. For outcome assessment, a couch and a stopwatch were used to facilitate standardized functional and pelvic floor muscle evaluations.

Outcome measures

To evaluate the effectiveness of the prehabilitation program on functional status, pelvic floor muscle performance, and recovery efficiency, standardized and clinically validated outcome measures were utilized. These measures were selected to comprehensively capture both functional and physiological changes associated with the intervention and to allow objective comparison between the intervention and control groups across the study period.

Brink Score: The Brink Score was used to evaluate pelvic floor muscle strength. The Brink score is a digital vaginal palpation scale used to assess pelvic floor muscle function by evaluating pressure (strength), duration (endurance), and vertical displacement (lift). With the patient in supine or crook-lying position, a gloved finger is inserted vaginally and the patient is instructed to contract the pelvic floor muscles. Each component is scored from 0 to 4, giving a total score of 0–12. Scores of 0–3 indicate severe weakness, 4–6 moderate weakness, 7–9 fair strength and 10–12 strong pelvic floor muscles.

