Karnofsky Performance Scale: The Karnofsky Performance Scale (KPS) is a standardized tool used to assess a patient's functional status and ability to perform daily activities, particularly in oncology and chronic illness care. KPS is widely used to evaluate disease severity, prognosis, treatment tolerance, and eligibility for therapies, and to monitor changes in functional capacity over time.

Duration of hospital: The duration of hospital stay was used as a measure of recovery efficiency. It was calculated as the number of days from the date of surgery to the date of hospital discharge, as documented in medical records. Shorter hospital stay was interpreted as improved recovery and functional readiness for discharge.

Data Analysis

The collected data were analyzed using SPSS with a significance level set at $p < 0.05$. Normality of continuous variables was assessed using the Shapiro–Wilk test, which indicated a non-normal distribution of the primary outcome measures, including Brink score and Karnofsky Performance Status (KPS). Due to the non-parametric nature of the data, within-group comparisons of pre and post-intervention scores were performed using the Wilcoxon signed-rank test, which is appropriate for evaluating paired differences in related samples when the assumption of normality is not met. Between-group comparisons at baseline and post-intervention were conducted using the Mann–Whitney U test, a non-parametric alternative to the independent samples t-test, suitable for comparing two independent groups with skewed data. Effect sizes were calculated to determine the clinical significance of observed changes in outcome measures. Recovery efficiency measured as hospital stay duration was summarized using descriptive statistics specifically mean and standard deviation to reflect the overall trend in postoperative recovery between groups. This combination of non-parametric tests and descriptive statistics ensured accurate and robust evaluation of the intervention's impact on pelvic floor strength, functional performance and recovery outcomes among post-surgical cervical cancer women.

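### Hospital stay, the only measure of recovery efficiency, gets a mean and SD with no between-arm estimate, interval or test, yet the plan claims a robust evaluation of recovery

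*Combined protocol and SAP*

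**What the plan says.** The title names pelvic floor weakness, functional performance and recovery efficiency. The opening paragraph of Outcome measures says the measures were selected "to allow objective comparison between the intervention and control groups across the study period". Under Duration of hospital, stay is "calculated as the number of days from the date of surgery to the date of hospital discharge", and a shorter stay is to be read as better recovery. No other measure of recovery efficiency is listed.

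The Data Analysis section reports non-normality for the primary outcomes, naming the Brink score and KPS. It then gives Wilcoxon signed-rank tests within groups and continues: "Between-group comparisons at baseline and post-intervention were conducted using the" Mann-Whitney U test. Effect sizes are mentioned for observed changes, with no type or interval given. Stay has its own sentence: "Recovery efficiency measured as hospital stay duration was summarized using descriptive statistics specifically mean and standard deviation", the purpose being "to reflect the overall trend in postoperative recovery between groups". The section closes: "This combination of non-parametric tests and descriptive statistics ensured accurate and robust evaluation of the" programme's effects, which it describes as the "impact on pelvic floor strength, functional performance and recovery outcomes".

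The Study procedure gives the trial size, "with 17 participants in each group", and lists the anticipated length of stay among the pre-test measurements as the assessment of recovery efficiency.

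**The concern.** The outcome was chosen so that the arms could be compared, but its stated analysis stops at summarising each arm. A mean and an SD describe the spread of stays among patients. They do not state how far the arms differ or how uncertain that difference is. If a shorter stay is read as better recovery, the natural use of two means is to see which is smaller, and with an ineffective programme the intervention mean would be the smaller about half the time.

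The closing sentence therefore promises more than the method delivers. A report that followed the plan as written could claim a recovery benefit from a numerical trend alone. This is avoidable, because patient-level stay is in the medical records and the arms are randomised.

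**Working it through.** **Does any planned comparison reach hospital stay?**

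- *Mann-Whitney test.* The sentence lists no outcomes. It follows the normality statement that names Brink and KPS, and it covers comparisons at baseline and after the intervention. Days from surgery to discharge can have no value four weeks before surgery. Stay then has a separate sentence confining it to mean and SD. The closing sentence sets non-parametric tests beside descriptive statistics as two different things, and stay is the only outcome assigned the latter.
- *Effect sizes.* These are tied to observed changes. Observed stay is a single post-surgical value, so it has no change score.
- *Per-arm summary.* That the mean and SD are given by arm is inferred from the reference to the groups. It is the reasonable reading.

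The likelier reading is that no between-arm estimate, interval or test is planned for stay.

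**How uncertain would the comparison be?** The plan gives no SD, effect size or power for its 34 participants, so there is no planned figure to reproduce.

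Inputs: n = 17 per arm (Study procedure); significance level 0.05 (Data Analysis), taken as two-sided; df = 17 + 17 − 2 = 32. SDs of 2, 3 and 4 days are assumptions.

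95% CI half-width for a difference in means = t(0.975, 32) × SD × √(2/17) = 0.699 × SD.

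Power comes from the noncentral t distribution with noncentrality d × √(17/2), where d is the difference divided by the SD. Power reaches 80% at d = 0.991.

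| Assumed SD (days) | CI half-width (days) | Difference with 80% power (days) | Power for a 1-day difference |
|---|---|---|---|
| 2 | 1.40 | 1.98 | 29% |
| 3 | 2.10 | 2.97 | 16% |
| 4 | 2.79 | 3.96 | 11% |

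The Mann-Whitney test, simulated on normal data with 20,000 replicates, had power of 28% at 0.5 SD and 78% at 1.0 SD, with size 5.05% under no difference. The t-test figures at the same two points are 29% and 81%, so the rank test changes little under normality.

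**How easily does a trend arise by chance?** With no true effect, the difference in means has standard error SD × √(2/17) = 0.343 SD. A gap of at least 0.25 SD in either direction is 0.25/0.343 = 0.73 standard errors, which occurs in about 47% of trials (normal approximation).

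**Multiplicity if a third between-arm test is added.** For independent tests at 0.05, the chance of at least one false positive goes from 1 − 0.95² = 9.8% to 1 − 0.95³ = 14.3%.

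**The case against.** The strongest reply is that the text does not strictly exclude a test. The Mann-Whitney sentence names no outcomes, the list of primary outcomes is introduced as non-exhaustive, and the authors themselves enter anticipated stay as a pre-test value, so they may have thought of stay as having a baseline. This stands as a statement of ambiguity. It weakens the argument from the missing baseline, but not the argument from the separate sentence confining stay to mean and SD. If a test was intended, the plan still needs to say so.

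A second reply is that descriptive reporting is acceptable for an outcome not named as primary, particularly when power for a 1-day difference is only 11% to 29%, and that readers can work out an approximate interval from means, SDs and n. Descriptive reporting would indeed be acceptable if the conclusions were limited to match. The plan does not label stay secondary or exploratory, does not commit to an interval, and claims a robust evaluation of recovery. Low power is a reason to show the interval.

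Three limits on the numbers are fair. The widths and power apply to any continuous outcome at this sample size. The half-width is for a difference in means, whereas a Hodges-Lehmann interval would have a somewhat different width that was not computed. The multiplicity figure counts only post-intervention between-arm tests and leaves out the plan's within-group and baseline tests.

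**Conclusion.** The concern holds and should be fixed. As written, the plan gives no inferential answer on one of its three title outcomes while claiming to evaluate it robustly. This rests on the likelier reading of the Mann-Whitney sentence; on the other reading, the text still needs a line saying that stay is compared.

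Any between-arm result would be imprecise: about ±0.70 SD at 95% confidence, with 80% power only near a 1 SD difference. Those figures assume a two-sided 5% level, equal SDs, roughly normal data and all 17 women per arm contributing. The values in days rest on the assumed SDs as well.

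The mismatch between anticipated and observed stay is minor. No analysis of change in stay is specified, so it needs only a clarifying line.

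**What to change.** In Data Analysis, state that observed days from surgery to discharge are compared between arms with the Mann-Whitney test already in the plan. Report the Hodges-Lehmann difference with its 95% CI, and give median and IQR beside mean and SD. Base any conclusion about recovery on that comparison, read mainly through the interval. The section is written in the past tense, so if stay data have already been seen, label the comparison as added.

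If stay is to remain descriptive, remove recovery outcomes from the closing sentence and make no claim of benefit on stay.

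In either case, state in the Study procedure that anticipated stay is descriptive only and is not a baseline value of the observed outcome.

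The cost is a few lines of text and one more comparison on data already collected. The result will probably be imprecise, it may need a post hoc label, and it adds a third between-arm test to a plan with no multiplicity control.
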